Latest approval: December 21 2017

Title:

Para-cervical block prior to laparoscopic hysterectomy as an adjuvant treatment to reduce postoperative pain.

Project Summary:

Hysterectomy is one of the most common surgical procedures performed in the United States. Adequate analgesia and a faster recovery from surgery have become key factors that have taken the front stage in recent years. Increased use of minimally invasive techniques as well as the implementation of adjuvant treatments such as TAP-block are examples of strategies that have come into play in order to reduce postoperative pain scores and hasten recovery. We propose the use of a paracervical block with bupivacaine performed prior to a hysterectomy as a method to further reduce postoperative pain. This is a prospective, blinded randomized controlled trial in which patients that are scheduled to undergo a laparoscopic hysterectomy would be allocated to one of two groups: Paracervical block with local anesthetic (bupivacaine 0.5%), or placebo. After the patient is placed under anesthesia, 10 mL of 0.5% bupivacaine would be injected into the cervical stroma at 3 and 9 o'clock, which is standard technique for para-cervical block. The remainder of the procedure will then continue in a regular fashion. Alternatively, patients in the control group will be injected with 10 mL of normal saline. The surgeon would be blinded as to patient allocation. At the end of the case, pain will be assessed using a visual analogue scale with a range from 0 to 10 by one of the researchers who will also be blinded to the group. This will be done at 30 and 60 minutes after surgical stop time. Additional pain control in the PACU will be standardized to all patients. We will use T-Student tests to assure groups are homogenous to age, BMI, operating time, history of cesarean deliveries, and uterine weight. Chi-square and Ancova analysis will be utilized to determine if there is a significant difference in reported pain scores between groups. We will also stratify subjects based on uterine weight, history of cesarean delivery, additional procedures, etc. and determine if this has an effect on the reported pain scores.

Hypothesis:

Performing a para-cervical block with local anesthetic prior to a laparoscopic hysterectomy significantly reduces pain after the procedure.

Specific aims:

Determine if infiltrating the cervical stroma with local anesthetic prior to performing a hysterectomy will reduce postoperative pain scores, and hence increase patient satisfaction.

Secondary aims:

Determine if there is a difference in baseline pain depending on additional procedures performed, and their response to the paracervical block.

Determine if there is a difference in response to paracervical block based on history of cesarean deliveries or uterine weight.

Background/Significance:

Hysterectomy is one of the most common surgical procedures performed in the United States, with more than 600,000 done annually. Over the last decade, there has been major changes in regards to the surgical approach utilized. With the advent of laparoscopy and robotic surgery, the rate of procedures done vaginally or abdominally has decreased significantly. One of the major drivers to this change is the demand for a faster recovery and decreased postoperative discomfort. Additionally, several adjuvant methods such as a TAP (transverse abdominal plain) block, ERAS (expedited recovery after surgery) pathway, etc. have been developed in order to minimize pain after surgery and hence increase patient satisfaction. Paracervical block is a particular technique that has been evaluated in multiple studies as a way to reduce pain after vaginal surgery. Studies have been successful in demonstrating an improvement in pain scores after these types of procedures. However, to our knowledge, there has never been follow-up to evaluate this method during the laparoscopic approach, with or without robotic assistance. The rationale of why this technique may be beneficial during a hysterectomy is that after infiltrating the cervical stroma with local anesthetic, it will diffuse towards the pelvic sidewalls via the lymphatic and capillary systems, which would allow for the anesthetic agent to come in direct contact with the nerve plexuses that innervate the pelvic structures. Safety of the technique has been proven over the years, given that it is widely used during office procedures that involve manipulation of the cervix. Although much of the focus regarding reducing postoperative pain has been centered on the abdominal wall and port sites, it is undeniable that a significant portion of pain actually arises from the pelvic surgical site; particularly since laparoscopic trocars have become smaller, resulting in less trauma. Our aim is to determine if infiltrating the cervical stroma with local anesthetic prior to performing a hysterectomy will reduce postoperative pain scores, and hence increase patient satisfaction.

Methods

Study design

This is a prospective randomized controlled trial in which patients that are scheduled to undergo a laparoscopic hysterectomy would be allocated to one of two groups: Paracervical block with local anesthetic (bupivacaine 0.5%), or placebo. This would be achieved using block randomization. The

intervention would be performed after the patient is under general anesthesia, prior to starting the surgery. Patients would be consented in the office or preoperative area (before receiving sedatives). As far as the intervention itself, it would consist of injecting 10 mL of 0.5% bupivacaine into the cervical stroma at 3 and 9 o'clock, which is standard technique for para-cervical block. The remainder of the procedure will then continue in a regular fashion. Alternatively, patients in the control group will be injected with 10 mL of normal saline. The surgeon would be blinded as to patient allocation. The formulations (saline or bupivacaine) will be previously prepared in a syringe in the operating room by a member of the research team prior to beginning the procedure. At the end of the case, pain will be assessed using a visual analogue scale with a range from 0 to 10 (Wong-Baker faces – appendix 1) by one of the researchers who will also be blinded to the group. This will be done at 30 and 60 minutes after surgical stop time. Additional pain control in the PACU will be standardized to all patients.

Study Subjects

Subjects will be selected based mainly on the fact they are undergoing a hysterectomy.

Inclusion criteria:

- Undergoing laparoscopic hysterectomy with or without salpingoophorectomy for benign indications
- Undergoing laparoscopic hysterectomy with robotic assistance with or without salpingoophorectomy for benign indications
- Between 18 and 60 years of age

Exclusion criteria:

- Intraoperative detection of malignancy
- Undergoing additional procedures at the time of surgery (except prophylactic McCall culdoplasty/uterosacral ligament suspension, excision of endometriosis, appendectomy, cystoscopy)
- Inability to perform paracervical block due to anatomic abnormalities (absent/flush cervix)
- Known allergy/sensitivity to bupivacaine
- Intraoperative bowel injury, bladder injury, ureter injury or major vessel injury that required repair.

Sample Size

Based on previous publications, it was determined that the expected mean pain score on postoperative day 0 after a TLH was 6 on the VAS, with a SD of 2. (10, 11) In order to detect

at least a 40% reduction in postoperative pain between groups, with a significance level of 5% and a power of 80%, a sample of 32 was required.

Data Collection

Data points to be collected are as follows:

- Age
- BMI
- Operating time
- History of cesarean deliveries
- Preoperative indication for surgery (pain, prolapse, tumor, bleeding, etc)
- Procedures performed (if ovaries/tubes were removed, if robotic assistance was used, if any additional procedures that are exceptions from the exclusion criteria were performed).
- Specimen weight
- Uterine pathology
- Pain score at 30 minutes (see appendix 1 for Wong-Baker scale)
- Pain score at 60 minutes
- Number of days in the hospital (zero if discharged on same-day)

Data Handling

A master key will be generated during randomization. It will contain patient initials and medical record number, and an individual code. Only the primary investigator will have access to this master key.

A separate de-identified database using the individual code as index will be used for collection of all data points. The data that can be collected on the day of surgery (baseline characteristics, operating time, pain scores, etc) will be collected that day using a standardized form (appendix 2). This will later be transferred to the de-identified database. Using the master key, we will research pathology reports when available to complete final data points (uterine weight, histology, etc).

The data-collection sheets will be destroyed as soon as they are transferred into the de-identified database.

Data Analysis

We will use T-Student tests to assure groups are homogenous to age, BMI, operating time, history of cesarean deliveries, and uterine weight. ChiSquare and Ancova analysis will be utilized to determine if there is a significant difference in reported pain scores between groups. We will also stratify subjects based on uterine

weight, history of cesarean delivery, additional procedures, etc. and determine if this has an effect on the reported pain scores.

Time Frame

We expect to be able to consent and enroll at least two patients per week (average range of hysterectomy procedures per week from the surgeons that will participate is 5-10). We expect the data collection phase to span over 30 weeks approximately.

Strength/Innovation

Patient satisfaction is a center point in today's healthcare. Faster recovery with less discomfort is not only standard of care, but may also translate into major economic advantages, such as less narcotic use and a decreased rate of postoperative admission. Using this technique as an adjuvant treatment for pain after laparoscopic hysterectomies has never been explored. There is data published for similar procedures, which demonstrates a clear benefit. If this study demonstrates significant improvement in pain scores, it has the potential to change standard of care for pain control during hysterectomy procedures.

Limitations

The main confounding factors are difference in operating style between surgeons and baseline surgical characteristics (large uteri that may require more dissection and tissue manipulation, etc.). To control for this we are only recruiting patients from 3 surgeons who have a similar operating technique. In addition to this, we are documenting operating time and specimen weight, which can be used to compare both groups and assure that they are homogenous to these potential confounders. Further analysis will also be made specifically stratifying the data based on these characteristics.

Risks

The risks of the procedure are minimal. Regarding possible adverse reactions to the local anesthetic, there is no additional risk given that this is already routinely administered during surgery. Patients will be screened to confirm they do not have a history of allergies to the medication. Possible reactions include hypotension, bradycardia, headaches, tremors, etc.

The paracervical block is routinely performed in the office setting before most invasive procedures involving the cervix, and risks are minimal, similar to those involving any subdermal injection. Possible risks include bleeding from injection site.

There is also the potential risk of accidental disclosure of the health information that will be collected.

Benefits

This study may find new methods of improving postoperative analgesia for patients undergoing minimally invasive hysterectomy procedures which may lead to less narcotic use, faster discharge from hospital, and greater satisfaction.

Costs

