12. ACOG Committee Opinion No. 444: choosing the route of hysterectomy for benign disease. *Obstet Gynecol.* 2009;114(5):1156-8.
13. Wong-Baker FACES Foundation (2016). Wong-Baker FACES® Pain Rating Scale. Retrieved 11/10/2016 with permission from <http://www.WongBakerFACES.org>.

Appendix 1

Wong-Baker FACES Pain Rating Scale (Used with permission)

©1983 Wong-Baker FACES Foundation. www.WongBakerFACES.org
 Used with permission. Originally published in Whaley & Wong's Nursing Care of Infants and Children. ©Elsevier Inc.

Appendix 2

Example of data collection form

Name:									Age:	MRN:	BMI:	
# of CDEL:	Indication(s) for surgery: 0 AUB 1 Pelvic pain 2 Prolapse 3 Fibroids 4 >4 Other: _____								Additional procedures performed: Oophorectomy Excision of endometriosis Vaginal vault suspension Minilap for tissue extraction Robotic Assistance YES NO			
Pain at 30 minutes: 0 1 2 3 4 5 6 7 8 9 10					Pain at 60 minutes: 0 1 2 3 4 5 6 7 8 9 10							
Days in hospital: 0 1 2 3 >3			Pathology: No abnormalities Adenomyosis Endometriosis Leiomyoma Other: _____					Spec weight: _____ grams	Operating time: _____ minutes

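### Uterine weight is recorded in grams but is to be analysed by strata with no cut point fixed; a continuous term with one pre-specified arm-by-weight test would be better protected and usually more efficient.

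*Combined protocol and SAP*

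**What the plan says.** The Project Summary and Data Analysis carry the same sentence: "We will also stratify subjects based on uterine weight, history of cesarean delivery, additional procedures, etc. and determine if this has an effect". It ends with reported pain scores as the outcome. Limitations, after naming operating time and specimen weight, adds: "Further analysis will also be made specifically stratifying the data based on these characteristics". The aim that needs more than an effect on pain is in Secondary aims: "Determine if there is a difference in response to paracervical block based on history of cesarean deliveries or uterine weight".

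The data form in Appendix 2 records weight as a number: "Spec weight: _____ grams". Operating time is likewise recorded in minutes. On timing, Data Handling has pain scores collected on the day of surgery, while for later items "we will research pathology reports when available to complete final data points (uterine weight, histology, etc".

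The only analysis that clearly uses weight as a measured value is the balance check: "We will use T-Student tests to assure groups are homogenous to age, BMI, operating time, history of cesarean deliveries, and uterine weight". The main analysis is described as "ChiSquare and Ancova analysis will be utilized to determine if there is a significant difference in reported pain scores between groups", with no covariates named. No section gives a cut point, a number of strata or a rule such as a median split. None says that strata will be defined before arms are revealed.

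**The concern.** Two separate things are at stake.

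- **Information.** Splitting a measured variable treats every uterus in a stratum as the same. If the block's effect changes gradually with weight, that discards part of the signal, in a trial that is small for any question about differential response.
- **Protection.** Strata on weight cannot be formed until pathology reports arrive, by which time the pain scores are recorded. Blinding is described for the surgeon and the pain assessor; nothing is said about when or by whom a cut would be set. With several plausible cuts available, a claim that the block works better or worse in large uteri could come from the choice of cut.

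This differs from asking whether an interaction test is planned at all. Adding one while leaving the cut free would leave the second problem in place.

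**Working it through.** **Inputs from Sample Size.** Control mean 6, SD 2, a 40% reduction (0.40 × 6 = 2.4 points), 5% significance, 80% power, sample 32.

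**The plan's own figure.** Two-sided normal approximation: n per arm = 2 × (1.96 + 0.84)² × 2² / 2.4² = 10.9, so 11 per arm and 22 in total. The exact t-test needs 12 per arm, 24 in total. Neither gives 32, and the plan does not say whether 32 is the total or per arm. The present point does not depend on this, so results are shown for totals of 32 and 64.

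**Assumptions not in the documents.** Two-sided tests, 1:1 allocation, weight normal on the log scale, and the size and shape of the weight effect.

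**Step 1: information kept by a median split.** The squared correlation between a normal variable and its median-split indicator is 2/π = 0.637. About 64% is kept and 36% lost if the relation is linear.

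**Step 2: what a split can detect.** The contrast in block effect between two halves has SE = 2 × √(4/c), with c patients per cell.

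- N=32, c=8: SE = 1.41. Detectable difference at 80% power = 2.80 × 1.41 = 4.0 points; power for a 2.4-point difference is 40%.
- N=64, c=16: SE = 1.00. Detectable difference 2.8 points; power for 2.4 points is 67%.

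**Step 3: power, continuous against median split.** Model: pain = 6 − 2.4·arm + b·arm·w + error (SD 2), where w is standardised log weight; the test is of the arm-by-weight term, with 3,000 simulated trials per setting (simulation error about one percentage point).

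| Change in block effect per SD of weight | N=32: continuous / split | N=64: continuous / split |
|---|---|---|
| 1.0 point | 26% / 18% | 47% / 32% |
| 1.5 points | 48% / 32% | 81% / 59% |

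Hand check for b = 1.5: the continuous interaction slope has SE of about 2 × √(4/N), which is 0.71 at N=32 and 0.50 at N=64. Normal-approximation power is then Φ(1.5/0.71 − 1.96) = 56% and Φ(1.5/0.50 − 1.96) = 85%. The simulated values are lower because they use the t distribution and let w vary. For the split, the halves differ in mean w by 2 × √(2/π) = 1.60 SD, so the contrast is 1.5 × 1.60 = 2.4 points. Step 2 gives 40% and 67% for that; the simulated 32% and 59% are lower because of the spread left within strata and unequal cells.

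At b = 0.5 and N=32 the two methods are nearly level, about 10% against 8-9%.

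**Step 4: a step instead of a line.** If the block effect changes by 2.4 points exactly at the median, the ranking reverses: about 23% continuous against 28% split at N=32, and 44% against 56% at N=64.

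**Step 5: false positives if the cut is picked for the smallest p value.** No true interaction; 6,000 trials for three and seven cuts, 1,200 for five.

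| Analysis | N=32 | N=64 |
|---|---|---|
| Continuous, one test | 5.2% | 5.2% |
| Fixed median split | 5.8% | 4.7% |
| Best of 3 cuts | 12.3% | 10.7% |
| Best of 5 cuts | 17.8% | 15.1% |
| Best of 7 cuts | 19.8% | 19.1% |

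A split fixed in advance holds its error rate; the inflation comes only from the choice.

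**The case against.** The strongest reply has four parts.

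- **Intent.** A reader might infer that the cut will be chosen with the pain scores in hand. The documents do not support that. They are silent on how and when strata are formed, and a median split or a cut set beforehand fits the text equally well. What stands is that nothing rules out a later choice.
- **Efficiency.** A reader might also infer that splitting is always the weaker method. That holds only for a roughly linear relation. Limitations speaks of large uteri needing more dissection, which could be read as a threshold, and under a step at the median the split does better. A 1.5-point change per SD is also a large assumption: around a 2.4-point mean benefit it implies a 5.4-point benefit at −2 SD and 0.6 points of harm at +2 SD. At 0.5 points the choice hardly matters.
- **Which question.** The stratifying sentence concerns "weight, history of cesarean delivery, additional procedures, etc. and determine if this has an effect on the reported pain scores", and Limitations concerns confounding. Only Secondary aims asks about response to the block, and all the figures above test that. This is fair. However, stratifying is the only method the plan offers that could serve that aim.
- **ANCOVA.** Its covariates are unnamed, so continuous weight is not excluded. It is not promised either, and as a main effect alone it would not address response to the block.

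**Conclusion.** The point holds as an inexpensive improvement to a secondary analysis. The plan's stated method for a variable recorded in grams is to stratify, with no cut fixed and with weight arriving after the outcomes. Under a roughly linear relation, a median split loses about 36% of the information, or 8 to 22 percentage points of power over the 1.0- and 1.5-point scenarios and both sample sizes. Under a step at the median it gains about 5 points at N=32 and 12 at N=64. The error inflation to about 11-20% applies only if the cut is actually picked as the best of three to seven; it describes what the wording permits and is not a forecast.

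A reader might take this as a threat to the trial's main result. It is not: the randomised comparison of pain between arms does not use the strata. Nor does the change rescue the secondary aim at N=32, where power stays below 50% under either form for the linear slopes considered. The case for a continuous term is that it removes the choice of cut and, if the relation is roughly linear, avoids discarding information.

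**What to change.** In the Project Summary, Data Analysis and Limitations, replace stratifying on uterine weight with the following.

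1. Enter uterine weight as a continuous term in the ANCOVA, for example log grams: alone for its effect on pain, and with one pre-specified arm-by-weight interaction for response to the block. Name in advance which of the two pain time points that test uses.
2. Label the interaction exploratory because its power is low, and report the estimate with its confidence interval.
3. Treat operating time, recorded in minutes, the same way.
4. If strata are shown in a table, fix the cut before arms are revealed, for example at the pooled median, and use them for display only.

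The cost is wording: the grams and minutes are already collected, and no patients, visits or data items are added. The downside is the assumption of a roughly linear relation on the chosen scale, which a plot can check only weakly at this sample size.

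### Pain levels by additional procedure are to be compared without using the indication for surgery, so pain that led to the operation could be attributed to the procedure

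*Combined protocol and SAP*

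**What the plan says.** The Project Summary and Data Analysis both state that the investigators will "stratify subjects based on uterine weight, history of cesarean delivery, additional procedures, etc. and determine if this has an effect on the reported pain scores". The first item under Secondary aims is: "Determine if there is a difference in baseline pain depending on additional procedures performed, and their response to the paracervical block". The second is: "Determine if there is a difference in response to paracervical block based on history of cesarean deliveries or uterine weight".

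The exclusion criteria define which concurrent surgery is allowed: "Undergoing additional procedures at the time of surgery (except prophylactic McCall culdoplasty/uterosacral ligament suspension, excision of endometriosis, appendectomy, cystoscopy". The form in Appendix 2 has its own list: "Additional procedures performed: Oophorectomy Excision of endometriosis Vaginal vault suspension Minilap for tissue extraction".

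Data Collection includes "Preoperative indication for surgery (pain, prolapse, tumor, bleeding, etc", and the form offers "Indication(s) for surgery: 0 AUB 1 Pelvic pain 2 Prolapse 3 Fibroids" (the digits appear to belong to the neighbouring caesarean-count box). On pain assessment, Study design says: "This will be done at 30 and 60 minutes after surgical stop time". Neither the data list nor the form has a preoperative score, so 'baseline pain' in the first aim can only mean postoperative pain.

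The indication is absent from three places where it might be expected:
- the balance tests, which name age, BMI, operating time, caesarean history and uterine weight;
- the named strata;
- the confounders in Limitations, which are surgeon style and surgical characteristics.

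ANCOVA is named for the pain scores, but its covariates are not.

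**The concern.** Randomisation makes the block and saline groups comparable. It does nothing for a comparison of women who had an additional procedure with women who did not, because the disease and the reason for surgery decide who gets one. A woman who has endometriosis excised is plausibly more likely than others to have come to surgery because of pelvic pain. If women with preoperative pain also report more pain at 30 and 60 minutes, the procedure group will score higher even when the procedure adds nothing.

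The plan words the question as one of effect. A confounded difference could thus be published as the answer to a declared secondary aim, although a variable that would reduce the problem is already on the form.

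**Working it through.** **No figure to reproduce.** The plan gives no number for this comparison, so the size is worked out under assumptions.

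**Inputs from Sample Size.** Control mean 6; SD 2; target reduction 40% × 6 = 2.4 points; sample 32. The text does not say whether 32 is the total or per group, so N = 32 and N = 64 are both shown.

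**Assumed inputs, none in the documents.** 35% of women have a pelvic pain indication; pelvic pain adds d = 1.0, 1.5 or 2.0 points after surgery; the true procedure effect is zero; allocation is 1:1.

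**Formula.** False difference = d × [P(pelvic pain | procedure) − P(pelvic pain | no procedure)].

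**Strong overlap: procedure in 60% of pelvic pain cases and 15% of others.**
- Share with a procedure: 0.35 × 0.60 + 0.65 × 0.15 = 0.2100 + 0.0975 = 0.3075.
- P(pelvic pain | procedure) = 0.2100 / 0.3075 = 0.68.
- P(pelvic pain | no procedure) = (0.35 × 0.40) / 0.6925 = 0.20.
- Gap = 0.48.

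The chance of p<0.05 comes from simulation (8000 runs per setting, two-sample t-test of procedure yes/no). Repeat runs differ by about one percentage point.

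| d | False difference | p<0.05, N = 32 | p<0.05, N = 64 |
|---|---|---|---|
| 1.0 | 0.48 | 8% | 12% |
| 1.5 | 0.72 | 12% | 19% |
| 2.0 | 0.96 | 16% | 29% |

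With arm and indication in the model, the bias is about 0 and the rate about 5%. That is partly by construction, since indication is the only confounder simulated.

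**Little overlap: procedure in 50% and 35%.**
- P(pelvic pain | procedure) = 0.1750 / 0.4025 = 0.43.
- P(pelvic pain | no procedure) = 0.1750 / 0.5975 = 0.29.
- Gap = 0.14, so the false difference is 0.14, 0.21 or 0.28 points. The rate is 5-6% for the first two and at most about 7%.

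**Does ANCOVA with arm alone help?** No. With 25% of women in the procedure stratum, pelvic pain in 80% versus 30%, and d = 2, the false difference is 2 × 0.5 = 1.0 point. A model with arm but not indication gives p<0.05 in 19% (N = 32) and 33% (N = 64). Adding indication brings both to about 6%.

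**Response to the block.** In the same set of simulations, the arm-by-stratum interaction test without indication kept a false-positive rate of 4-6%, provided indication did not itself change the block effect.

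**Precision after adjustment (strong overlap).** The large-sample standard error of the adjusted difference is 2 / √(N × v), with v = 0.35 × 0.60 × 0.40 + 0.65 × 0.15 × 0.85 = 0.167.
- N = 32: 0.87, so the 95% half-width is 2.05 × 0.87 = 1.8 points.
- N = 64: 0.61, so 2.00 × 0.61 = 1.2 points.

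Allowing for chance variation in cell counts, simulation gives about 1.9 and 1.3. At N = 32 the mean standard error was 0.93 adjusted and 0.93-0.97 crude, so adjustment did not widen the interval here.

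**The case against.** The strongest reply is that the plan never says the comparison will be crude. ANCOVA is named with its covariates open, and the strata end in an open 'etc.', so use of the indication is neither planned nor ruled out. That stands as far as it goes: the confounded result could be reported, and nothing shows that it would be. But an open list leaves the choice until the data have been seen.

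Second, additional procedures are a mixed group. Culdoplasty or uterosacral suspension, appendectomy, cystoscopy, oophorectomy and minilaparotomy have no stated link with pelvic pain, and pooling them with excision of endometriosis could shrink the gap. This also stands, and it is why the little-overlap case is shown.

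Third, the adjusted interval is wider than the bias it removes: about ±1.9 points against at most about 1 point at N = 32. On the assumed rates, the adjustment there rests on about 32 × 0.35 × 0.40 = 4.5 pelvic pain patients without a procedure and 32 × 0.65 × 0.15 = 3.1 other patients with one. The comparison is exploratory either way. Imprecision is still no reason to keep an avoidable bias.

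Finally, the first aim can be read as descriptive. The sentence in the Project Summary and Data Analysis, however, asks about an effect.

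**Conclusion.** The point holds for pain level by additional procedure. Omitting the indication could produce a false difference from about 0.1-0.2 points, which is negligible, to about 1 point with strong overlap, where the false-positive rate is 16% (N = 32) or 29% (N = 64). Everything numerical rests on assumed prevalences and an assumed effect of pelvic pain; the documents cannot narrow the range.

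A reader might infer more, and the documents do not support it:
- **That the main result is confounded.** Block versus saline is randomised, overall and within each stratum. Only the causal reading of a difference in response between strata would need care, if indication changes the block effect.
- **That uterine weight and caesarean history share the problem.** The second aim asks about response to the randomised block by these factors. For uterine weight the case is weak: the indication on the form closest to a heavy uterus is fibroids rather than pain, so the direction of any bias is uncertain. For caesarean history no mechanism is apparent.
- **That the bias is large.** Harsher inputs (d = 3; pelvic pain in 90% versus 20%) give 3 × 0.7 = 2.1 points, but nothing in the documents points to them.

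This is an inexpensive improvement to a secondary analysis and does not threaten the primary comparison.

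**What to change.** In Data Analysis, and in the matching sentence of the Project Summary:

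- Compare pain level by additional procedure with a linear model for each pain score (30 and 60 minutes) containing arm, additional procedure (yes/no, stating which entries count) and pelvic pain as an indication (yes/no).
- Report the adjusted difference with its 95% CI and call it an association, not an effect.
- Keep the response-to-block questions of both secondary aims as separate arm-by-factor interaction terms. The model above has no such term and would otherwise drop them.

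The cost is a few lines of text and no new data, since the form already records the indication. The downsides are one more covariate in a small trial, estimates that stay imprecise, and possibly a wider interval if indication and procedure overlap even more strongly than assumed. Adjustment removes only what the yes/no indication captures; without a preoperative score, differences in pain severity remain.
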